
 To test whether LPV/r is associated with decreased viral shedding from self-collected nasal swabs over 14 days compared to placebo 	
 Proportion of days with SARS-CoV-2 detected from mid-nasal swabs by PCR Median quantity of SARS-CoV-2 detected from mid-nasal swabs by PCR
Exploratory	

 To assess pharmacokinetics and exposure-response relationship of LPV/r 	
 LPV/r blood concentration in DBS

COVID-19: coronavirus disease; DBS: dried blood spot; Flu-PRO: inFLUenza patient-reported outcome; LPV/r: lopinavir-ritonavir; LRTI: lower respiratory tract infection; SARS-CoV-2: severe acute respiratory syndrome coronavirus 2; SpO2: blood oxygen saturation level; WHO: World Health Organization.
	

Sample Size:

The study will enroll 173 participants per arm to achieve 80% statistical power at 2-sided type I error rate of 5% for a pairwise comparison against the control to detect a treatment effect of hazard ratio of 1.5 for the primary outcome(s) assuming control event rate of 60% for the primary outcome and 5% dropout rate. Additional controls will be added to allow for contemporaneous controls for the LPV/r arm. Eligible participants will be randomized at a 1:1 ratio LPV/r + and Ascorbic acid. If a second eligible patient is in the same household, both will be assigned to the same regimen. A blinded sample size re-assessment may be done to possibly increase the target sample size, conditional on the observed incidence rate and within household correlation. Should a new intervention be added, the randomization ratio may be adjusted to favor the new arm, ensuring that control arm participants are still enrolled concurrently with active arms; an empirical Bayesian information borrowing method may be used to incorporate past control arm data for the comparison of new intervention that is added later.

Duration:

Twenty-eight days of clinical follow-up per participant.

Proposed Sites (up to 6): University of Washington, Tulane, Boston University, Cook County, and others to be discussed

2. Schedule of Activities

Procedure	Screening	Self-quarantine									EOS	
		Treatment Period										
	Day 0 ^a	Day 1 ^a	Day 2 ^a	Day 3	Day 4 ^a	Days 5 to 8	Day 9 ^a	Days 10 to 13	Day 14 ^a	Day 21	Day 28 ^b	
Informed consent	X											
Demography	X											
Sign HIPAA form	X											

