7.5. Method of Treatment Assignment

Participants will be randomized in a 1:1 ratio to placebo (ascorbic acid), or LPV/r, at the level of the household (all eligible participants in 1 household will receive the same intervention). The randomization plan will be overseen by the Study Statistician. The randomization code and resulting allocation list will be generated and overseen by the Study Statistician. The list will be blocked and stratified by site and risk level.

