11.1.1. COVID-19 Endpoints

Overall sample size will depend on the number of events observed. To detect at least a 1.5-fold increased risk of the COVID-19 symptom resolution rate under a null hypothesis of no reduction

and four interim monitoring analyses with stopping for futility and efficacy based on the O'Brien-Fleming bounds and 80% power, the trial is designed to achieve 99 events per pairwise comparison for the symptom resolution endpoints. To achieve this, 173 participants will be enrolled per arm.

As the initial sample size target, 210 per arm was chosen for each experimental group (HCQ, HCQ + azithromycin), assuming a control arm rate of approximately 30% and 5% dropout rate.

HR (active/control)	Events/arm	N per arm	Median control arm (days)	Median active arm (days)*
1.4	142	247	10	7
1.5	99	173	10	7
1.6	75	129	10	6
1.7	59	103	10	6
1.8	49	85	10	6
1.9	41	71	10	5
2,0	36	63	10	5

*Under constant baseline hazard assumption

11.1.2. *Viral Shedding Endpoint*

Assuming the median time to cessation of viral shedding is 10 days and a constant baseline hazard for cessation of shedding, approximately 62% of participants would no longer experience viral shedding at 14 days under the null hypothesis of no intervention effect. Assuming 420 participants per pairwise comparison, 90% statistical power, 1-sided type I error rate of 2.5% for efficacy, we can detect at least a 37% increase in the rate of cessation of viral shedding. Under an extreme example of having only half that sample, 210, we could detect an increase of 54% or higher.

11.2. *Populations for Analyses*

For analysis purposes, the following populations are defined and will be described in greater detail in the trial Statistical Analysis Plan:

Population	Description
Intention to Treat (ITT)	All enrolled participants
Modified ITT	All enrolled participants who do not have LRTI at Baseline: high-risk group for the primary clinical endpoint; high- and low-risk groups (separately) for the primary virologic endpoint.
PK evaluable	Participants from the DBS sub-study with at least 1 interpretable PK sample.

DBS: dried blood spot; PK: pharmacokinetic; PCR: polymerase chain reaction; SARS-CoV-2: severe acute respiratory syndrome coronavirus 2.

11.3. *Statistical Analyses*

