The Statistical Analysis Plan will be developed and finalized before database lock and will describe the participant populations to be included in the analyses, the detailed analytical plans with endpoints and procedures for accounting for missing, unused, and spurious data. An Interim Monitoring Plan will also be developed to describe approaches for re-estimation of sample size and any planned interim analyses. This section presents a brief summary of the planned statistical analyses of the primary and secondary endpoints (these are listed in [Section 4](#)).

11.3.1. *Efficacy Analyses*

Demographic characteristics (age, sex, race) of each study group will be tabulated.

The mean age (plus range and standard deviation) by sex of the enrolled participants, as a whole and per group, will be calculated.

Primary analyses: The primary analyses will be conducted on the intend-to-treat population overall and by cohort (high-risk and low-risk). Participants randomized to each active treatment will be compared to participants randomized to placebo (ascorbic acid). If appropriate, the primary analysis will make use of all participants randomized to placebo, whether contemporaneously enrolled or not, using an Empirical Bayesian information borrowing method (described below). Due to anticipated heterogeneity in risk of disease progression, pre-specified baseline variables, including age, BMI, and days of symptoms at time of enrollment will be included in the model to increase precision.

Both primary endpoints will be analyzed using a Cox proportional hazards model with robust standard errors, adjusted for within household correlation.

As-treated analysis: The primary analyses will be repeated, replacing randomization arm by actual treatment to account for possible off-label use of and noncompliance to the investigational products.

Subgroup analyses: All subgroup analyses will be pre-specified in the Statistical Analysis Plan. Any further subgroup analyses will be considered ad hoc.

Missing Data

Due to the design of the study and retention activities, measurable outcomes are expected for all participants. However, in the unlikely event of a missing test result, the missing data will be imputed.

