2.2. ANALYSIS COHORTS AND DATA SETS

This section describes the cohorts and corresponding datasets for the primary, secondary and exploratory analyses described in this document. In the definitions below, cohort refers to the study participants included in a dataset; whereas the datasets further specify which visits are included from the specified cohort. All data sets include the baseline variables specified in Section 2.1 and are included as guidance, recognizing that in practice, what is listed as a single data set may actually require sets of data sets (for example repeated vs single time point outcomes for secondary outcomes) depending on the analysis.

Intention to Treat (ITT) Cohort: The ITT Cohort includes all participants enrolled into the study.

Modified Intention to Treat (mITT) Cohort: The mITT Cohort includes all participants enrolled into the study who completed the day 1 (enrollment) questionnaire.

Viral Shedding (VS) Data Set This data set will include all participants in the cohort with all data required for primary and secondary viral shedding endpoints.

Hydroxychloroquine (HCQ) Secondary Efficacy Data Set This data set will include all participants in the cohort randomized to hydroxychloroquine or contemporaneous control and secondary endpoints.

Hydroxychloroquine + azithromycin (HCQ+A) Secondary Efficacy Data Set This data set will include all participants in the cohort randomized to the combination hydroxychloroquine/azithromycin arm or its contemporaneous control and secondary endpoints.

Hydroxychloroquine (HCQ) Safety Data Set This data set will include all participants in the cohort randomized to hydroxychloroquine or contemporaneous control and secondary outcomes.

Hydroxychloroquine + azithromycin (HCQ+A) Safety Data Set This data set will include all participants in the cohort randomized to the combination hydroxychloroquine/azithromycin arm or its contemporaneous control and safety outcomes.

Hospitalized Data Set This data set will include all participants who reported a COVID-19-related hospitalization within the planned 28 days of follow-up.

Modified Intention to Treat (ITT) High Risk (HR) Cohort: The ITT HR Cohort includes all mITT cohort participants enrolled into the study's high risk cohort.

Hydroxychloroquine (HCQ) Efficacy Data Set This data set will include all participants in the cohort randomized to hydroxychloroquine or contemporaneous control.

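### The primary LPV/r analysis may borrow placebo participants from the stopped HCQ stage by a method that neither document describes, with no rule for when or how much

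*Protocol*

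**What the plan says.** Protocol Section 11.3.1 compares each active arm with placebo. It adds that, where appropriate, the primary analysis will take in all placebo participants "whether contemporaneously enrolled or not, using an Empirical Bayesian information borrowing method (described below"). The synopsis likewise says that past control data may be borrowed for an intervention added later.

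Nothing after that sentence describes the method. The same section specifies a Cox model with robust standard errors for both primary endpoints. The covariates it names are age, BMI and days of symptoms; calendar time and trial stage are not among them. The SAP contains no borrowing method and states in its introduction that it covers the first three arms.

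The synopsis also provides for a full concurrent control group: "Additional controls will be added to allow for contemporaneous controls for the LPV/r arm". Section 7.5 says "Participants will be randomized in a 1:1 ratio to placebo (ascorbic acid), or LPV/r, at the level of the household". The size is "173 participants per arm to achieve 80% statistical power at 2-sided type I error rate of 5" percent, for a hazard ratio of 1.5, "assuming control event rate of 60% for the primary outcome and 5% dropout rate".

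**The concern.** Section 5.1 says that the HCQ arms were stopped and LPV/r was added by this amendment. Any placebo participant not contemporaneous with LPV/r therefore comes from the HCQ stage. This is an inference from Sections 5.1 and 11.3.1 read together, but no other source exists.

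The documents show three differences between the stages:

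- Period: HCQ-stage enrolment stopped on 28 July 2020 (SAP Section 5).
- Eligibility: the HCQ and azithromycin exclusions no longer apply (Section 6.2).
- Placebo: the platform's control was ascorbic acid with or without folic acid (Sections 3 and 5.1); for LPV/r it is ascorbic acid alone.

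Randomisation protects the comparison of LPV/r with its concurrent controls, but not the borrowed part. If symptoms resolve or virus clears faster or slower in the later period for any reason, some of that shift is credited to or charged against LPV/r.

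The choice is also left open late. Section 11.3 requires the SAP to be final only before database lock, and Section 7.6.1 leaves the study statistician unblinded for analysis. Whether borrowing is appropriate, and how strongly, could thus be settled while arm-level data are accessible.

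**Working it through.** **1. Does the concurrent comparison carry the stated power?**

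Inputs: hazard ratio 1.5, 80% power, two-sided 5%, control event rate 60%, dropout 5% (synopsis); 99 events and 173 per arm (table in Section 11.1.1).

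- N per arm: 99 / (0.60 × 0.95) = 173.7, against 173 stated.
- Events: Schoenfeld's formula gives 191 in total. With an inflation of about 1.028 for five O'Brien-Fleming looks this is 196, or 98 per arm. Freedman's formula gives 197.
- Power with 2 × 99 = 198 events: Φ(ln 1.5 × √198 / 2 − 1.96) = 81%, or about 80% after the interim looks.

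The plan's figure is reproduced from concurrent controls alone. This reads 99 as events per arm, as the table column does. The text says "the trial is designed to achieve 99 events per pairwise comparison for the symptom resolution endpoints"; 99 events in total would give only 52% power, so the table label is the one that fits.

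**2. What could drift do?**

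Assumptions, none given in the documents: the number of earlier controls (50 to 210; the planned HCQ-stage figures were 165 per arm in the SAP and 210 in the protocol, but that stage stopped early), and the drift r, the ratio of resolution rates in the LPV/r stage to those in the HCQ stage. Normal approximation on the log hazard scale, ignoring household clustering and covariates:

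- e = 99 events per concurrent arm; h = 0.57 × earlier controls; w = weight given to them
- bias = [w·h / (e + w·h)] × ln r
- test SE = √[1/e + 1/(e + w·h)]
- true SD = √[1/e + (e + w²·h)/(e + w·h)²], which equals the test SE when w = 1

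Worked case, full pooling, 165 earlier controls, r = 1.2: h = 94.05; share = 94.05/193.05 = 0.487; bias = 0.487 × 0.1823 = 0.0888, a spurious hazard ratio of 1.09; SE = 0.1236; bias/SE = 0.72; two-sided error = Φ(−1.24) + Φ(−2.68) = 11.1%.

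Two-sided type I error at a nominal 5%:

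| Borrowing | r = 1.1 | r = 1.2 | r = 1.3 |
|---|---|---|---|
| Full pooling, 80 earlier controls | 5.6% | 7.3% | 9.7% |
| Full pooling, 165 | 6.6% | 11.1% | 17.9% |
| Half weight, 80 | 4.7% | 5.2% | 6.0% |
| Half weight, 165 | 4.9% | 6.6% | 9.1% |

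**3. A discounted method, closer to what the protocol names**

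An illustrative normal-normal empirical Bayes estimator with a moment-estimated between-stage variance (400,000 simulations per case) gives, for 50 / 100 / 165 / 210 earlier controls:

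- r = 1.2: 5.7% / 6.5% / 7.6% / 8.2%
- r = 1.3: 6.0% / 7.1% / 8.3% / 8.8%

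**4. Power under full pooling, same four sizes**

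- No drift: 86% / 88% / 91% / 92%, against 81% without borrowing.
- Drift of 1.2 in the opposite direction: 78% / 75% / 73% / 71%.

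**The case against.** Several points on the other side stand.

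- The borrowing is conditional in both places where it appears. A reader might infer that earlier controls will be pooled regardless; the text does not say so. What is missing is the condition itself.
- A reader might take 17.9% as the expected error rate. It assumes full pooling, which is not the named method, and 165 earlier controls, a planned number for a stage that stopped early. At half weight with drift of 1.1 there is no inflation.
- A reader might infer that the SAP contradicts the protocol, since its data sets take participants "randomized to hydroxychloroquine or contemporaneous control". Those data sets concern the HCQ arms only. They set no rule for LPV/r.
- The remark in SAP Section 1.2 that understanding of disease progression changed is about knowledge. It does not show that outcomes drifted.
- The changed clinical endpoint adds little. The viral-clearance definition is the same in both stages, and SAP Section 7.3 analyses HCQ-stage symptom resolution on nearly the same criteria. The protocol also says that folic acid has no known antiviral activity.
- A reader might infer that neither primary endpoint needs borrowing. Step 1 shows this only for symptom resolution. Section 11.1.2 bases shedding power on 420 participants per comparison, while 2 × 173 = 346.

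It can also be said that borrowing is a declared platform feature, that Section 11.3 is a summary, and that a later LPV/r SAP could supply the method. That is possible, but no such SAP is among the documents. Writing out the method would close the specification gap. It would not give the borrowed controls the protection of randomisation.

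**Conclusion.** The point holds in this form: the plan as written can let non-randomised controls into the primary LPV/r result without a trigger, a discount rule or a stage term, although the concurrent arm alone meets the stated power for symptom resolution (198 events, about 81% before interim looks). This is more than a missing detail, because it leaves open which control group defines the primary result.

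The harm is possible and not demonstrated. Its size depends on three unknowns: the number of earlier controls, the drift and the borrowing rule. The full-pooling figures are a worst case over the ranges shown; a discounting method would do less damage without removing the bias. Adjustment for age, BMI and symptom days may absorb some change in case mix, but not a calendar-time effect as such. The documents do not establish that drift occurred or that borrowing will be used.

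**What to change.** In Section 11.3.1, state that the primary LPV/r comparison uses only placebo participants randomised concurrently with LPV/r. Move borrowing to a labelled, pre-specified sensitivity analysis. Replace the empty cross-reference with the method itself: the model, the discounting rule, the condition for using it, and a stage or calendar-time term. Align the synopsis sentence on past control data, and carry the same text into the SAP that will cover LPV/r.

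This is a change of wording, with no added participants or procedures. Its cost is the precision that borrowing would bring if there were no drift: under full pooling, symptom-endpoint power would rise from about 81% to 86–92%. That gain lies beyond the design target and depends on an assumption the trial has not tested. Whether 346 participants suffice for viral shedding, given the 420 assumed in Section 11.1.2, is a separate matter to settle on its own terms.

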11.3.2. Secondary Endpoints

All secondary endpoints will be assessed in the Intention-to-Treat population overall and by cohort.

11.3.2.1. Safety Analyses

All safety analyses will be performed on the Intention-to-Treat population. AEs will be compared by study group.

11.3.2.2. Disease Severity

Disease severity, as measured by the WHO Ordinal Scale for Clinical Improvement ([Appendix 11](#)), will be compared between the groups using a proportional odds model.

Disease severity over the first 14 days and at Days 21 and 28 will also be measured by the modified Flu-PRO survey ([Appendix 12](#)). Results will be analyzed as for the WHO Ordinal Scale for Clinical Improvement.

Progression and regression of disease severity will be modeled using multistate models.

11.3.3. Pharmacokinetic Analysis

Sparse PK from DBS will be analyzed using standard population PK analysis methodologies using standard software such as NONMEM[®] version 7.4 or Phoenix NLME version 8.2.

11.3.4. Exploratory Exposure-Response Analyses

PK-evaluable participants will have post-hoc individual concentration profiles and exposure estimates determined for exploratory exposure-response analyses against primary and secondary efficacy and safety endpoints. Exploratory PK/pharmacodynamic analyses will be performed as the data allow.

COVID-19	Coronavirus disease
CQ	Chloroquine
CYP	Cytochrome P450
CYP3A	Cytochrome P450 3A
DAIDS	Division of Acquired Immunodeficiency Syndrome
DBS	Dried blood spot
DSMB	Data and safety monitoring board
EC ₅₀	Half-maximal effective concentration
ECG	Electrocardiogram
eCRFs	Electronic case report forms
Eligible	Qualified for enrollment into the study based upon adherence to inclusion/exclusion criteria
FDA	Food and Drug Administration
Flu-PRO	InFLUenza patient-reported outcome
GCP	Good Clinical Practice
GFR	Glomerular filtration rate
HCQ	Hydroxychloroquine
HIPAA	Health Insurance Portability and Accountability Act
HIV	Human immunodeficiency virus
IATA	International Air Transport Association
ICF	Informed consent form
Index case	Term used throughout the protocol to denote the person with confirmed or suspected SARS-CoV-2 infection to whom the study participant was exposed
IRB	Institutional Review Board
LPV/r	Lopinavir-ritonavir
LRTI	Lower respiratory tract infection
MERS-CoV	Middle East respiratory syndrome coronavirus
Participant(s)	Term used throughout the protocol to denote the enrolled individual(s)
PBPK	Physiologically based pharmacokinetics
PCR	Polymerase chain reaction

PEP	Post-exposure prophylaxis
PK	Pharmacokinetic(s)
QTc	Heart-rate corrected QT interval
RNA	Ribonucleic acid
SAE	Serious adverse event
SARS-CoV	Severe acute respiratory syndrome coronavirus
SARS-CoV-2	Severe acute respiratory syndrome coronavirus 2
SoA	Schedule of Activities
SpO2	Oxygen saturation
USPI	United States prescribing information
WHO	World Health Organization
WIRB	Western Institutional Review Board

Appendix 2: Protocol Structure

The protocol for this trial will be structured to be modular. Given the perpetual nature of this trial, there may be modifications and/or additions to the main protocol. Each modification and/or addition to the main protocol will be subject to the data and safety monitoring board who will receive recommendation from other study committees (see [Appendix 3](#)).

The main protocol will contain all the background and rationale for this trial and all generic information to the trial, the research approach, the trial design and conduct, and the overall trial governance, and ethical considerations. Other appendices for study governance, site-specific protocol addendum template, hydroxychloroquine (HCQ) label, azithromycin label, lopinavir-ritonavir label, pharmacokinetic modelling, and pharmacokinetic sample collection and analysis are provided below. The Intervention-Specific Appendices (e.g., HCQ label appendix) will contain the information about the interventions. There will be a specific appendix for each of the intervention arm with features of the given intervention strategy and how it will be delivered, and any additional endpoints and data collection that are not covered in the Main Protocol.

Study conduct will be monitored by an independent monitor. Monitors will visit participating clinical research sites, or schedule equivalent virtual visits, to review the individual participant records, including consent forms, electronic case report forms, supporting data, laboratory specimen records, and endpoints through laboratory and medical records (physicians' progress notes, nurses' notes, individuals' hospital charts), to ensure protection of study participants, compliance with the protocol, and accuracy and completeness of records. The monitors also will inspect the sites' regulatory files to ensure that regulatory requirements are being followed and the sites' pharmacies to review product storage and management.

Data and Safety Monitoring Board

An independent data and safety monitoring board (DSMB) will be convened for this study with expertise in coronavirus disease (COVID-19) or respiratory viruses, antiviral therapies and shedding, and emerging epidemics and a biostatistician. The purpose of the DSMB is to monitor the study for operational futility, social harms, and efficacy. The DSMB will evaluate the progress of the project, including periodic assessments of accrual, retention, safety, performance and variation of the project sites, and other factors that can affect project implementation.

The DSMB will review and approve modifications to the overall enrollment target based on the event rate. Due to the anticipated rapid speed of enrollment and the short duration of the study, it is unlikely that pre-specified stopping rules for efficacy and futility in terms of the efficacy of hydroxychloroquine (HCQ), HCQ + azithromycin, or lopinavir-ritonavir will be reached before all participants are enrolled. The DSMB will review severe acute respiratory syndrome coronavirus 2 (SARS-CoV-2) endpoints.

The DSMB will conduct interim reviews (if specified) when adequate data have been accrued and convene by teleconference. Open reports containing accrual and retention rates, participant characteristics, and serious adverse events will be sent to the protocol team and DSMB members the week prior to the DSMB meeting. Only the DSMB members and the unblinded biostatistician will receive password-protected closed reports of SARS-CoV-2 endpoints by randomization arm.

Regulatory and Ethical Considerations

The study will be conducted according to GCP, the Belmont Report, and the Declaration of Helsinki. The study protocol, site-specific informed consent forms (ICFs), participant education and recruitment materials, and other requested documents—including any subsequent modifications—will be reviewed and approved by Western Institutional Review Board (WIRB), as the single IRB of record, responsible for oversight of research conducted at the study sites. Subsequent to initial review and approval, the WIRB will review the study at least annually.

Informed Consent Process

The principles of informed consent in the current edition of the Declaration of Helsinki will be implemented in each clinical study before any protocol-specified procedures or interventions are carried out. The consent form will describe the purpose of the study, the procedures to be followed, and the risks and benefits of participation. A copy of the consent form will be given to the participant, and this fact will be documented in the participant's record.

A participant who is rescreened is not required to sign another ICF; eligibility for the study must be re-checked prior to enrollment.

Study Records

Each study site will establish a standard operating procedure for confidentiality protection. Each site will ensure that study records including administrative documentation and regulatory documentation as well as documentation related to each participant enrolled in the study, including ICFs, locator forms, case report forms, notations of all contacts with the participant, and all other source documents are stored in a secure manner.

Confidentiality

Participants' study information will not be released without their written permission, except as necessary for oversight by:

- The protocol Principal Investigators or designees
- Study funders
- WIRB
- University of Washington IRB

All laboratory specimens, evaluation forms, reports, and other records that leave the site will be identified by coded number only to maintain participant confidentiality. The exceptions are SARS-CoV-2 testing results, which are subject to local and state reporting which is name-based. Local public health may contact participants diagnosed with SARS-CoV-2 for the purpose of surveillance and contact notification. Participants will be informed prior to SARS-CoV-2 testing that results are reportable and may lead to contact by local public health if results are positive for infection.

All records will be kept locked. After initial acquisition of data, all computer entry and networking programs will be done with coded numbers only. Clinical information will not be released without written permission of the participant, except as necessary for monitoring by the IRB, Office for Human Research Protections, other local, United States, and international regulatory entities as part of their duties or the industry supporters or designees.

